2.4 Assessment of Objectives

Consistent with the primary objectives, the **primary endpoints** are:

Safety

- All Adverse Events (AEs) assessed by the investigator to be related to the Dapivirine Vaginal Ring-004.

- All Grade 3 and 4 AEs.
- All Serious Adverse Events (SAEs).

Adherence

Residual amounts of dapivirine in returned rings and/or dapivirine concentrations in plasma and/or dapivirine concentrations in vaginal fluid.

The primary endpoints will be assessed through:

Safety

All product-related AEs, Grade 3 or 4 AEs, SAEs, physical examination, gynaecological assessments, including pelvic/speculum examination, laboratory tests and other indicated investigations.

Adherence

- Determined dapivirine residual amounts in returned used vaginal rings and/or
- Measured concentrations of dapivirine in plasma [**Not implemented**] and/or
- Measured concentrations of dapivirine in vaginal fluids [**Not implemented**.]

Consistent with the secondary objectives, the **secondary endpoints** are:

- The HIV-1 seroconversion rate per 100 woman-years of product use at the end of the vaginal ring use period.
- HIV-1 drug resistance mutations among participants who acquire HIV-1 infection.

The secondary endpoints will be assessed through:

- Rapid and specialised laboratory testing according to a pre-specified HIV testing algorithm.
- Viral genotype resistance testing methods which include sensitive methods to detect low frequency drug-resistant variants (only population genotyping will be done.)

Consistent with the exploratory objectives, the **exploratory endpoints** include:

- Feasibility of a 3-monthly clinical follow-up schedule.
- Dapivirine residual amounts in returned used vaginal rings and/or dapivirine concentrations in plasma and/or vaginal fluid in correlation with results from the visual inspection of the returned used vaginal rings by research staff.
- Proportion of participants opting for HIV rapid tests at the research centre between scheduled 3-monthly research centre follow-up visits.
- The proportion of women who report the use of the vaginal ring as acceptable.
- Participant self-reported patterns of ring use.

The exploratory endpoints will be assessed through:

- Participant report of feasibility regarding a 3-monthly clinical follow-up schedule (Participant Questionnaire).
- Number of women opting not to receive two additional rings at the 3-monthly visits.

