9 EVALUATION OF TRIAL ENDPOINTS

9.1 Primary Endpoint 1 – Safety

The analysis of AEs will be mainly descriptive in nature. That is, the number and percentage of participants experiencing AEs will be presented per SOC and PT, overall and by research centre. The proportion of participants experiencing the following will be determined and summarized:

- AEs considered by the Investigator as related to IP
- Grade 3 or 4 AEs
- SAEs

For these three endpoints, and for the most frequently reported AEs (*i.e.* AEs occurring in at least 5% of participants overall) the proportion and the corresponding 95% confidence interval will be presented for the overall counts. The confidence interval will be determined using Fisher's exact test.

Separate tabulations will be created for AEs of special interest (selected urogenital AEs and STIs). For this purpose, PTs may be grouped into categories of interest (refer to Appendix 5).

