10.1.2 Product-related Adverse Events

Product-relatedness is reported as “Related” or “Not Related”. While every effort is made to ensure that this field is not missing through data reviews and queries, if the relationship with the IP is missing on the CRF, it will be assumed that the AE was “Related” to the IP.

Summary Tables

A summary table of TEAEs will be presented, indicating the frequency and proportion of participants with:

- At least one TEAE
- At least one serious TEAE
- At least one Division of Acquired Immunodeficiency Syndrome (DAIDS) Grade 3 or 4 TEAE
- At least one product-related TEAE
- At least one serious product-related TEAE
- A TEAE leading to death
- A TEAE leading to premature (permanent) IP discontinuation
- A TEAE leading to temporary IP discontinuation
- A TEAE leading to trial discontinuation.

If meaningful, the same summary tables may be produced for non-TEAEs.

The definitions and location of data elements to be used to define each measure are described in Table 2 below.

Table 2 Definition and Data Sources of AEs

Measure	Statistic	Data Sources*
Participants with at least one TEAE	Frequency	A participant reported with an AE in the AE CRF Source: AE
Participants with at least one serious TEAE	Frequency	A participant reported as having an SAE per the AE CRF Source: AE

Measure	Statistic	Data Sources*
Participants with at least one DAIDS Grade 3 or 4 TEAE	Frequency	A participant reported as having a DAIDS Grade 3 or 4 AE Source: AE
Participants with at least one product-related TEAE	Frequency	A participant reported as having a “related” event, per the AE CRF Source: AE
Participants with at least one serious product-related TEAE	Frequency	A participant reported as having a “related” SAE, per the AE CRF Source: AE
Participants with a TEAE leading to death	Frequency	A participant reported as having an AE with the reported outcome “fatal” per the AE CRF Source: AE
Participants with a TEAE leading to premature (permanent) IP discontinuation	Frequency	A participant reported as having an AE with an action taken of “drug withdrawn” per the AE CRF Source: AE
Participants with a TEAE leading to temporary IP discontinuation	Frequency	A participant reported as having an AE with an action taken of “drug interrupted” per the AE CRF Source: AE

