Participants with a TEAE leading to trial discontinuation	Frequency	A participant reported as having a Trial Completion status of “Participant discontinued from the trial early” and a reason of “Adverse event/intercurrent illness” per the TC CRF Source: TC

* Percentages will use the total number of enrolled participants as denominator.

A by-participant listing of all TEAEs will include the variables in Table 3 below.

Table 3 AE Variables

Variable	Data Type	Data Sources
SAE	Dichotomous	Yes/No Source: AE
Outcome	Nominal	Fatal, Not recovered/not resolved, Recovering/resolving, Resolved/recovered w/sequelae, Recovered/resolved, Unknown Source: AE
Severity	Ordinal	Grade 1 Mild, Grade 2 Moderate, Grade 3 Severe, Grade 4 Potentially life-threatening, Grade 5 Death Source: AE
Relationship	Ordinal	Related, Not related Source: AE
Action	Nominal, DDMMYY	Dose not changed, Drug interrupted, Drug withdrawn, N/A Date interrupted, date reintroduced, date withdrawn

Variable	Data Type	Data Sources
		Source: AE
Other action	Nominal	None, Treatment medication, Non-drug therapy, Other Source: AE
SOC	Nominal	System Organ Class Source: AE
PT	Nominal	Preferred Term Source: AE
AE Term (Verbatim)	Nominal	Reported Event Source: AE

The incidence of TEAEs will be presented by SOC and PT, overall, IPM 027 treatment arm and by research centre.

The incidence of the following TEAEs by severity will be presented by SOC and PT, overall, IPM 027 treatment arm and by research centre:

- TEAEs
- Serious TEAEs
- Product-related TEAEs
- Serious product-related TEAEs
- Social harms reported as TEAEs (refer to Section 10.9).

In addition, for IPM 027 participants who directly enrolled in the IPM 032 trial from the open-label treatment period of IPM 027, a subgroup display of Overall TEAEs, TEAEs by worst severity and Product-related TEAEs will be presented.

Maximum severity will be assumed for an AE with missing severity.

A by-participant listing of all deaths, SAEs, non-TEAEs, permanent IP discontinuations and premature trial discontinuations will be presented in Appendix 16 of the CSR. These by-participant listings will include variables described in the summary of TEAEs in addition to the following variables:

Table 4 Additional AE Variables

Variable	Data Type	Data Sources
AE start date	DDMMYY	Start date Source: AE
Outcome date	DDMMYY	Outcome date Source: AE
Trial day	Continuous	Trial day = (Start Date of AE – Date of First Use of IP) + 1 Source: Calculated from AE (AESTDAT) and ENR

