Preferred name 1	n (%) ^b	X (X.X)	X (X.X)	...	X (X.X)	X (X.X)
Preferred name 2	n (%) ^b	X (X.X)	X (X.X)	...	X (X.X)	X (X.X)
...						

Programmers Note: Please repeat for each drug name class and preferred term

Percentages are calculated out of the number of participants (per centre) ^a In the safety population ^b Reported prior medication

Prior medication is defined as any medication that started and ended before the first insertion of the investigational product (IP)

Medications were coded using WHO DDE (version June 2017)

Centre 01: Madibeng Centre for Research (MCR); Centre 02: MatCH Research Unit (MRU); Centre 04: Qhakaza Mbokodo (QM);

Centre 06: MRC/UVRI & LSHTM Uganda Research Unit (MRC/UVRI); Centre 07: Desmond Tutu HIV Foundation (DTHF), Masiphumelele; Centre 08: Ndlovu Care Group (NCG)

Table 14.3.1.1
Overall Summary of Treatment Emergent Adverse Events
Safety Population

Subgroup: All IPM 032 participants

Statistic	Centre 01				All Centres		
	IPM 027 (N=XXX)	Dapivirine (N=XXX)	IPM 027 Placebo (N=XXX)	IPM 032 Overall (N=XXX)	IPM 027 (N=XXX)	Dapivirine (N=XXX)	IPM 027 Placebo (N=XXX)
	IPM 032 Overall (N=XXX)
At least one TEAE	n (%) ^a	X (X.X)	X (X.X)	X (X.X)	...	X (X.X)	X (X.X)
At least one serious TEAE	n (%) ^a	X (X.X)	X (X.X)	X (X.X)	...	X (X.X)	X (X.X)
At least one DAIDS Grade 3 or 4 TEAE	n (%) ^a	X (X.X)	X (X.X)	X (X.X)	...	X (X.X)	X (X.X)
At least one product-related TEAE	n (%) ^a	X (X.X)	X (X.X)	X (X.X)	...	X (X.X)	X (X.X)
At least one serious product-related TEAE	n (%) ^a	X (X.X)	X (X.X)	X (X.X)	...	X (X.X)	X (X.X)
TEAEs leading to death	n (%) ^a	X (X.X)	X (X.X)	X (X.X)	...	X (X.X)	X (X.X)
TEAEs leading to permanent IP discontinuation	n (%) ^a	X (X.X)	X (X.X)	X (X.X)	...	X (X.X)	X (X.X)
TEAEs leading to temporary IP discontinuation	n (%) ^a	X (X.X)	X (X.X)	X (X.X)	...	X (X.X)	X (X.X)
TEAEs leading to trial discontinuation	n (%) ^a	X (X.X)	X (X.X)	X (X.X)	...	X (X.X)	X (X.X)
Urogenital TEAEs	n (%) ^a	X (X.X)	X (X.X)	X (X.X)	...	X (X.X)	X (X.X)
Social harms reported as TEAEs	n (%) ^a	X (X.X)	X (X.X)	X (X.X)	...	X (X.X)	X (X.X)
Non TEAEs	n (%) ^a	X (X.X)	X (X.X)	X (X.X)	...	X (X.X)	X (X.X)

Programmers Note: Please repeat table for the following subgroup: IPM 027 participants who directly enrolled in IPM 032 (Note that the number of participants in the headers (N=XXX) should reflect the number of participants in each subgroup)

IP = Investigational product; TEAE = Treatment emergent adverse event

Deaths are not included in summary

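### The footnote to the overall TEAE summary (Table 14.3.1.1) excludes deaths and so contradicts that table's own fatal-TEAE row; Grade 5 events also need a visible row beside the Grade 3 and 4 endpoint

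*SAP*

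**What the plan says.** The table shells in SAP Appendix 1 include Table 14.3.1.1, which summarises TEAEs by centre, by IPM 027 arm and overall, and is repeated for women who enrolled directly from IPM 027. Its rows include women with any TEAE, with a serious TEAE, with a Grade 3 or 4 TEAE, and "TEAEs leading to death". Beneath it stands the footnote "Deaths are not included in summary". The footnote names no row and gives no reason. It does not say whether it removes fatal events or women who died.

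The body of the SAP points the other way. The list of contents for this summary in SAP 10.1.2 includes "A TEAE leading to death". Table 2 defines that row: "A participant reported as having an AE with the reported outcome" of fatal on the AE form. Neither place mentions an exclusion.

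On severity, SAP 2.4 gives the primary endpoint as "All Grade 3 and 4 AEs", as does Protocol 2.2, and SAP 9.1 analyses "Grade 3 or 4 AEs". Table 3 of SAP 10.1.2 records severity on a five-point scale: "Grade 1 Mild, Grade 2 Moderate, Grade 3 Severe, Grade 4 Potentially life-threatening, Grade 5 Death". Table 14.3.1.4 and Listing 16.2.7.7 cover Grades 3 and 4 only. The worst-severity tables (14.3.1.7 to 14.3.1.11) run to Grade 5.

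**The concern.** Safety is one of the two primary objectives, and Table 14.3.1.1 is its overall summary. A programmer who applies the footnote produces a table with no fatal TEAEs, next to a listing of TEAEs leading to death (16.2.7.8) that may not be empty. The serious-TEAE count could then also differ from Table 14.3.1.5 in the same population, and the any-TEAE count from Table 14.3.1.2. A programmer who follows SAP 10.1.2 produces correct counts under a footnote that misdescribes them.

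The severity issue is separate and does not arise from the footnote. The recording scale goes one step beyond the endpoint, and no rule says where a Grade 5 event is shown beside it. A reader of Table 14.3.1.4 alone could take it to hold every woman with an event of Grade 3 or worse, which it does not if any event is recorded as Grade 5.

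**Working it through.** The plan gives no figure on this point, and no formal sample size or power calculation was done, so there is nothing to reproduce. The check is one of consistency, followed by a small illustration of size.

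**Step 1: trace one case.** Take a woman whose only TEAE is fatal and is recorded as Grade 5. Protocol 7.4.1 makes an event that results in death an SAE.

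| Output | Footnote followed | Footnote ignored (SAP 10.1.2, Table 2) |
|---|---|---|
| 14.3.1.1, any TEAE | 0 | 1 |
| 14.3.1.1, serious TEAE | 0 | 1 |
| 14.3.1.1, fatal TEAE | 0 | 1 |
| 14.3.1.1, Grade 3 or 4 | 0 | 0 |
| 14.3.1.2, any TEAE | 1 | 1 |
| 14.3.1.4, Grade 3 or 4 | 0 | 0 |
| 14.3.1.5, any serious TEAE | 1 | 1 |
| 14.3.1.7 and 14.3.1.8, Grade 5 column | 1 | 1 |
| Listing 16.2.7.8 | listed | listed |

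The first three rows show the contradiction. The two Grade 3 or 4 rows are zero under either reading, so the footnote neither causes nor cures that gap.

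**Step 2: when the counts actually fall.** If the footnote removes fatal events, the any-TEAE count falls only for a woman whose sole TEAE was fatal. The serious-TEAE count falls for a woman whose sole serious TEAE was fatal, even if she had other, non-serious events. The fatal row falls to zero. If the footnote instead removes women who died, each such woman leaves every row she would otherwise have entered. The shell does not say which is meant.

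**Step 3: size of the footnote effect.** Input: the planned total of about 1400 women (SAP 3.2). One woman is 1/1400 = 0.0714%, or 0.07 percentage points, shown as 0.1 at the one decimal that SAP 6.6 sets. The numbers of deaths below are assumptions, because the documents give none. Intervals are exact (Clopper-Pearson) 95% limits.

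- Row emptied: 0/1400 = 0%, upper limit 0.26%.
- One fatal TEAE: 1/1400 = 0.07% (0.002 to 0.40).
- Three fatal TEAEs: 3/1400 = 0.21% (0.04 to 0.63).

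**Step 4: size of the severity gap.** Assume that 50 women have a Grade 3 or 4 TEAE, and that a further 0, 1, 3 or 5 women have a Grade 5 event as their only severe event.

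- Grade 3 or 4 only: 50/1400 = 3.57% (2.66 to 4.68).
- Grade 3 or higher, one more: 51/1400 = 3.64% (2.72 to 4.76).
- Three more: 53/1400 = 3.79% (2.85 to 4.92).
- Five more: 55/1400 = 3.93% (2.97 to 5.08).

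The shifts are well inside the intervals. What is at issue is the visibility of a fatal event and agreement between tables, not precision.

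**The case against.** The strongest reply is that the shell does not settle on an exclusion. It contradicts itself, and the body of the SAP resolves the conflict: SAP 10.1.2 and Table 2 require the fatal row, and SAP Section 1 calls the appendices supporting material. The footnote may mean only that deaths as such are not tallied here, since Table 14.1.1.1 counts death as a reason for leaving the trial. This stands as far as it goes. An always-empty fatal row is the outcome of one reading, not an established fact. But the footnote as worded carries no such limit, and on the mild reading it is still misleading.

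A reader might also infer that deaths drop out of the safety analysis. The documents do not support that. A fatal event is an SAE, so it counts in the primary SAE endpoint, whose confidence interval is in Table 14.3.1.5 with no exclusion note. It also counts in Table 14.3.1.2 and in the Grade 5 columns, and SAP 10.1.2 calls for a listing of all deaths.

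On severity, a reader might infer that the endpoint is wrong and must become Grade 3 or higher. That goes too far. Grades 3 and 4 are the protocol's pre-specified endpoint, the SAP repeats it faithfully, and death is captured by the separate SAE component. Widening it would change a primary endpoint and would need an entry in SAP 11, which declares no changes. Nor is every fatal event missed: Listing 16.2.7.7, confined to Grades 3 and 4, allows a fatal outcome, and the fallback criteria in Protocol 7.2 stop at potentially life-threatening. The gap exists only for events actually recorded as Grade 5.

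**Conclusion.** The point holds as an internal contradiction in one table shell. The footnote to Table 14.3.1.1 cannot stand beside the fatal-TEAE row or SAP 10.1.2. If applied, it empties that row and can put the any-TEAE and serious-TEAE counts below those in Tables 14.3.1.2 and 14.3.1.5; the error can go only downward. The primary SAE result is not affected under either reading.

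The severity point holds as a presentation gap, conditional on a woman's only severe event being recorded as Grade 5. It is not an error in the endpoint.

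Numerically both are small: 0.07 percentage points per woman at 1400, more in a centre or subgroup column with a smaller denominator. This rests on the planned enrolment and on an unknown number of deaths. If no TEAE was fatal, no count changes, but the footnote would still be inconsistent with the table it annotates.

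**What to change.** Delete the footnote from Table 14.3.1.1 so that fatal TEAEs count in every row to which they belong, as SAP 10.1.2 and Table 2 already require.

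Keep the Grade 3 and 4 endpoint as the protocol defines it. Add one supplementary row, either Grade 3 or higher or Grade 5 alone, to Tables 14.3.1.1 and 14.3.1.4, labelled as supplementary. When programming it, settle one related mismatch: SAP 10.1.2 gives a missing severity the maximum, while the worst-severity shells set it to 4 on a scale that ends at 5. Unless the two agree, ungraded events could enter a Grade 5 row by default.

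The cost is one footnote and one extra row. No new data are needed and no primary endpoint changes. SAP Section 1 waives signature only for formatting changes to the appendices, so by implication the added row would need sign-off on the revised shells.

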IPM 011 was an open-label, crossover trial conducted in South Africa and Tanzania among sexually active women to assess the safety and acceptability of a silicone elastomer placebo vaginal ring (containing no active ingredient), intended as a microbicide delivery method for the prevention of HIV infection. Participants were randomly assigned in a 1:1 ratio to one of two trial groups. Both groups participated in two regimens: a placebo vaginal ring regimen and an observational safety regimen (with no placebo vaginal ring). Each regimen had 12-week duration. Eighty-two percent (82%) of women in this trial reported no ring removals at all for the entire duration of the trial, across trial groups and visits, and 99% of participants reported wearing the ring for at least 80% of the days they were meant to. Eighteen percent (18%) of women self-reported at least one ring removal or expulsion during the course of trial participation. This proportion increased to 22% when pharmacy records were incorporated. Many of the reported expulsions and removals were related to menses, e.g. heavy blood flow or concern about the ring becoming dirty or retaining odour, leading to removal. Ninety-five percent (95%) of women found the ring to be very comfortable. All questionnaire responders were willing to use the vaginal ring if shown to be effective for HIV prevention⁶.

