3.1. Trial Design

IPM 032 is a Phase IIIb, multi-centre follow-on open-label trial to evaluate the continued adherence to and safety of the Dapivirine Vaginal Ring-004, inserted at monthly intervals in healthy, HIV-negative women who have participated in the IPM 027 Phase III Dapivirine Vaginal Ring-004 trial. All women who have participated in IPM 027 and are HIV-negative at screening for IPM 032 will be eligible. An estimate of approximately 1400 participants will be enrolled. All participants will receive the dapivirine vaginal ring containing 25 mg dapivirine (Ring-004) at enrolment and will attend a research centre follow-up visit one month after enrolment. Following this visit, at investigator's discretion, a participant can continue on a 3-monthly visit schedule. Monthly visits may however be extended up to the first three months of participation. Once the 3-monthly trial visit schedule commences, three rings will be dispensed. One ring will be self-inserted at the research centre and two additional rings will be dispensed for the participant to take home, or dispensing will take place as arranged with the participant.

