In instances where the date of IP initiation, *i.e.* the start date of ring use, is missing or unknown, the missing date will be imputed with the date of the enrollment visit.

In accordance with the protocol, each scheduled visit has a window period of \pm 7 days. If the participant does not return to the research centre for a scheduled visit prior to the start of the trial window of the next visit, the visit will be considered missed. If a participant presents for a visit outside the window for a scheduled trial visit, but prior to the start of the window for the next visit, it will be treated as a late visit. Missed visits and late visits will be documented as protocol deviations (refer to Section 7.2). Data recorded at late visits will be analysed as pertaining to the scheduled visit. Unscheduled visits may be performed at any time during the trial. If an unscheduled visit takes place within any given window period and any repeat observations are made within the given window period, the repeat values will be captured as pertaining to the unscheduled visit. Data from scheduled and unscheduled visits will be shown in the participant listings, and listings will be appropriately labelled when data arise from unscheduled visits. Data from scheduled visits will be presented in the summary tables.

Visit Schedule A will consist of participants who attend Trial Month Visits 1, 4, 7, 10, 13, and 16/Exit; Visit Schedule B will consist of participants who attend Trial Month Visits 1, 2, 5, 8, 11, 14, and 17/Exit; and Visit Schedule C will consist of participants who attend Trial Month Visits 1, 2, 3, 6, 9, 12, and 15/Exit.

Tables, figures, and listings of trial results will accompany the text of the CSR. Listings of all clinical data recorded in the CRFs will be provided, except for those CRFs which are used for administrative purposes, such as the Participant Encounter Form (PEN) and the End of Trial Inventory (ETI). Listings will be sorted by research centre and participant identification number (PID), and key variables such as visit date and/or trial visit number will be presented in each listing.

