10.6.2 Summary Tables

Results from pregnancy tests will be presented in tabular form overall, by IPM 027 treatment arm and by research centre for each trial visit and will include appropriate statistics. A table including the following summaries will be included:

- Proportion of pregnancies
- Pregnancy incidence rates by contraceptive method (DMPA, norethisterone, oral contraception, etc.)
- Pregnancy incidence rates by outcome (full term live birth, premature term live birth, etc.).
- Pregnancy incidence rates per 100 person-years
- Frequencies of congenital anomalies

By-participant listings will be provided for each participant.

Table 9 Pregnancy Tests

Variable	Data Type	Data Sources
Type of test (urine or serum)	Dichotomous	Source: PHTR

Pregnancy Test	Dichotomous	Source: PHTR
----------------	-------------	--------------

Results from HIV tests will be presented in tabular form overall, by IPM 027 treatment arm and by research centre for each trial visit and will include appropriate statistics. By-participant listings will be provided for each participant, including whether the participant HIV-1 seroconverted (confirmed), the date of seroconversion, the time to seroconversion, and whether HIV-1 infection occurred while using IP.

Table 10 HIV Tests

Variable	Data Type	Data Sources
HIV Test Result (Test #1)	Dichotomous	Source: PHTR
HIV Test Result (Test #2)	Dichotomous	Source: PHTR
HIV Test Result (Test #3)	Dichotomous	Source: PHTR
HIV-1 Western Blot	Nominal	Source: SER
Repeat HIV-1 Western Blot	Nominal	Source: SER
HIV-2 Western Blot	Nominal	Source: SER
Repeat HIV-2 Western Blot	Nominal	Source: SER
RNA PCR Testing	Nominal	Source: electronic lab data *Only tested for HIV-1 seroconverters

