Safety Population

LPUV Question	Statistic	IPM 032 Overall (N=XXX)
Participants who responded positively to the following Do you think it is possible for women to use the ring as requested (i.e. without removing it)?	n (%) ^a 95% CI ^b	X (X.X) XX, XX
Do you think women in your community would want to use this ring if it were available?	n (%) ^a 95% CI ^b	X (X.X) XX, XX

CI = Confidence interval; LPUV = Last product use visit

^a Percentages are calculated out of the number of participants in the safety population

^b 95% CI calculated using Fisher's exact test

A participant will be classified as having found the vaginal ring acceptable if she responds positively to the first question, about keeping the ring inserted as prescribed. Community acceptability will be demonstrated by positive responses to the second question

Table 14.3.5.7
 Accidental Ring Expulsion/ Removal
 Safety Population

Visit	Reason Ring Was Removed / Came Out	Statistic	IPM 032 Overall (N=XXX)
Trial Month X	Participants who had an accidental ring removal/expulsion	n (%) ^a	X (X.X)
	Participants who had no accidental ring removals/expulsions	n (%) ^a	X (X.X)
...			

^a Percentages are calculated out of the number of participants in the safety population

Table 14.3.6.1
Vital Signs
Safety Population

Parameter (unit) Visit	Statistic	Centre 01				All Centres		
		IPM 027 Dapivirine (N=XXX)	IPM 027 Placebo (N=XXX)	IPM 032 Overall (N=XXX)	...	IPM 027 Dapivirine (N=XXX)	IPM 027 Placebo (N=XXX)	IPM 032 Overall (N=XXX)
Parameter (unit)								
Baseline	n	XXX	XXX	XXX	...	XXX	XXX	XXX
	Mean	XX.X	XX.X	XX.X	...	XX.X	XX.X	XX.X
	(q1,med,q3)	(XX.X,XX.X,X X.X)	(XX.X,XX.X,X X.X)	(XX.X,XX.X,X X.X)	...	(XX.X,XX.X,X X.X)	(XX.X,XX.X,X X.X)	(XX.X,XX.X,X X.X)
	SD	XX.XX	XX.XX	XX.XX	...	XX.XX	XX.XX	XX.XX
	(Min, Max)	(XX, XX)	(XX, XX)	(XX, XX)	...	(XX, XX)	(XX, XX)	(XX, XX)
LPUV	n	XXX	XXX	XXX	...	XXX	XXX	XXX
	Mean	XX.X	XX.X	XX.X	...	XX.X	XX.X	XX.X
	(q1,med,q3)	(XX.X,XX.X,X X.X)	(XX.X,XX.X,X X.X)	(XX.X,XX.X,X X.X)	...	(XX.X,XX.X,X X.X)	(XX.X,XX.X,X X.X)	(XX.X,XX.X,X X.X)
	SD	XX.XX	XX.XX	XX.XX	...	XX.XX	XX.XX	XX.XX
	(Min, Max)	(XX, XX)	(XX, XX)	(XX, XX)	...	(XX, XX)	(XX, XX)	(XX, XX)
Change from baseline to LPUV	n	XXX	XXX	XXX	...	XXX	XXX	XXX
	Mean	XX.X	XX.X	XX.X	...	XX.X	XX.X	XX.X
	(q1,med,q3)	(XX.X,XX.X,X X.X)	(XX.X,XX.X,X X.X)	(XX.X,XX.X,X X.X)	...	(XX.X,XX.X,X X.X)	(XX.X,XX.X,X X.X)	(XX.X,XX.X,X X.X)
	SD	XX.XX	XX.XX	XX.XX	...	XX.XX	XX.XX	XX.XX

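### Table 14.3.5.7 reports accidental ring expulsion/removal as a percentage of women per visit, although the look-back lengthens from one month to three and the denominator ignores who was due at that visit

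*SAP*

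**What the plan says.** Protocol section 3.1 brings every woman back one month after enrolment and then allows a 3-monthly schedule at the investigator's discretion; "Monthly visits may however be extended up to the first three months of participation". SAP section 6.6 turns this into three schedules. The shortest monthly phase is the first: "Visit Schedule A will consist of participants who attend Trial Month Visits 1, 4, 7, 10, 13, and 16/Exit". Women on Schedule B have a further monthly visit at Month 2 before moving to 5, 8, 11 and 14. Those on Schedule C are seen monthly up to Month 3, then at 6, 9 and 12. In each case the exit visit follows three months after the last of these.

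Table 14.3.5.7 in SAP Appendix 1 has a Visit column with rows for Trial Month X. It prints n (%) for "Participants who had an accidental ring removal/expulsion", with a companion row for women without such an event. Its footnote reads "Percentages are calculated out of the number of participants in the safety population". No row shows the number of women seen, the length of the interval or the time on the ring.

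SAP section 9.4.4, which covers self-reported patterns of ring use (an exploratory endpoint), promises only descriptive summary tables for expulsions and removals. It defines no rate.

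**The concern.** A count of women with any event since the last visit depends on how long ago that visit was. When a woman moves from monthly to 3-monthly visits, her reporting interval triples, so the percentage rises even if her behaviour does not change.

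The switch is also when women start changing rings at home. A step in the table at that point therefore invites a behavioural explanation.

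The fixed denominator adds a second distortion. A row such as Month 5 holds only Schedule B women in its numerator but divides by everyone, so it can look reassuringly low for no reason connected with ring use. The shell does not say whether women not due that month count as event-free in the companion row.

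**Working it through.** The tables are empty shells, so there is no planned figure to reproduce. The check asks what the table would show if nothing changed over time.

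**Inputs.** The visit months are those in SAP section 6.6. The illustrative risk comes from Protocol section 1.4.3, on an earlier open-label crossover trial of a placebo ring with a 12-week ring regimen: "Eighteen percent (18%) of women self-reported at least one ring removal or expulsion during the course of trial participation". The same section gives 22% once pharmacy records are added. Twelve weeks is treated as three months. The shares of women on Schedules A, B and C are not given, so they are varied.

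**Step 1: women seen, constant independent risk.** With three-month risk q, the monthly risk is p = 1 − (1 − q)^(1/3), and the inflation at the switch is [1 − (1 − p)^3] / p.

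- q = 18%: p = 1 − 0.82^(1/3) = 6.4%; ratio 18 / 6.4 = 2.81.
- q = 22%: p = 7.95%; ratio 2.77.
- Assumed p of 1%, 5%, 10% and 20%: ratios 2.97, 2.85, 2.71 and 2.44.

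**Step 2: women seen, events clustered in repeat expellers.** Let each woman's monthly rate follow a gamma distribution with shape k and mean m. Choose m so that the three-month figure stays at 18%: m = k(0.82^(−1/k) − 1)/3. The one-month figure is then 1 − (1 + m/k)^(−k).

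- k = 0.5: 7.25% per month; ratio 2.48.
- k = 0.2: 8.58% per month; ratio 2.10.

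**Step 3: the percentage as the shell defines it.** For each month, sum over the schedules attending: share × [1 − (1 − p)^L], where L is months since the previous scheduled visit. The denominator is the whole safety population. With p = 6.4% and full retention, Month 1 is 6.4% under every mix. Multiples of Month 1 are in brackets.

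| A/B/C share (%) | Month 4 | Month 5 | Month 6 |
|---|---|---|---|
| 100/0/0 | 18.0% (2.81) | none due | none due |
| 90/5/5 | 16.2% (2.53) | 0.9% (0.14) | 0.9% (0.14) |
| 80/10/10 | 14.4% (2.25) | 1.8% (0.28) | 1.8% (0.28) |
| 50/25/25 | 9.0% (1.41) | 4.5% (0.70) | 4.5% (0.70) |
| equal thirds | 6.0% (0.94) | 6.0% (0.94) | 6.0% (0.94) |
| 10/10/80 | 1.8% (0.28) | 1.8% (0.28) | 14.4% (2.25) |

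The pattern repeats every three months. Months 2 and 3 still have a one-month look-back, but they also fall. At 80/10/10 they print 1.28% (0.20) and 0.64% (0.10), because most women were not due.

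**Step 4: exposure basis.** Dividing events by ring-months of use gives a ratio of 1.0 across the switch at constant risk, whatever the schedule mix.

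**The case against.** The best defence is that this is one descriptive shell, and that the weightier adherence summaries are already scaled. Residual drug is tabulated by month of ring use with rings as the denominator (Table 14.3.5.2). Self-reported adherence is days worn over days expected (Table 14.3.5.5). That is true and limits the damage, but neither table measures how often rings come out.

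The size is also illustrative: it borrows a figure from a placebo ring and assumes a constant risk. Clustering lowers the ratio to about 2.1 to 2.5, though not to 1. Some event dates will be unknown, so a rate needs a rule for them.

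Four stronger readings are tempting, and the documents do not support them.

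- **The printed series will climb about threefold.** A reader might infer this, but the fixed denominator means it may fall instead.
- **Pregnancy reporting has the same fault.** SAP section 10.6.2 says "Results from pregnancy tests will be presented in tabular form overall, by IPM 027 treatment arm and by research centre for each trial visit", but the same section and Table 14.3.7.4 also plan a rate per 100 person-years, which visit spacing does not distort. A urine test shows current status, not events over a look-back, and Protocol section 5.6 keeps pregnant women on the visit schedule.
- **The questionnaire item on removal mixes intervals.** It appears in separate tables for Months 2 and 3 (14.6.6) and for 3-monthly follow-up (14.6.8).
- **The feasibility conclusion is biased.** SAP section 9.4.1 assesses feasibility through questionnaire answers, women declining the extra rings and the proportion of rings returned. Expulsion is not among these measures.

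**Conclusion.** The point stands for Table 14.3.5.7 only. As specified, its rows are not comparable with one another, and no other planned summary corrects for time on the ring.

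Among women seen, a constant monthly risk of up to 10% produces a rise of 2.7 to 3 times at the switch (2.8 times for the 18% illustration), or about 2.1 to 2.5 times under strong clustering. As printed, the three-month rows run from 0.14 to 2.81 times Month 1 over the mixes tried, with no change in behaviour. The direction cannot be predicted because the schedule mix is not given.

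These sizes assume a constant risk, full retention, and that each event is counted at the next scheduled visit. The shell does not say how an event reported at an interim ring-collection visit would be counted. The consequence is a misleading display for an exploratory endpoint; it does not affect a primary result. It should still be corrected, because the table would mislead if produced exactly as written.

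**What to change.** Replace the by-visit percentage in Table 14.3.5.7, and add matching text to SAP section 9.4.4, as follows.

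- Report expulsion/removal events per 100 ring-months of use, by month of ring use, split into the monthly and the 3-monthly phase.
- Within each month of ring use, report women with at least one event on the same ring-month basis.
- Take event dates from the Accidental Expulsion/Removal Log (Listing 16.2.5.5) and exposure from the Ring Insertion/Removal Log (Listing 16.2.5.4).
- Where an event date is unknown, assign the event to the ring dispensed at that time. The footnote to Listing 16.2.5.2 already uses this convention.
- If by-visit rows are kept, divide by the women seen at that visit, print that number, and print the look-back length (one or three months) in each row.

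The cost is SAP and shell wording plus programming. No new data are needed.
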